 - Group 1 will take by mouth three 1000 mg capsules twice a day (6000 mgs) of MSM plus standard of care naproxen.
 - Group 2 will take by mouth three placebo capsules twice a day plus standard of care naproxen.
- Subjects will be asked to complete the following questionnaires:
 - RMDQ
 - PIQ-6
- Subjects will be asked “On a scale of 0-10, with 10 being the worst pain, what is your current level of pain”.
- Subjects will be asked if they are undergoing any other treatment for back pain, when the last treatment was, and whether or not they were satisfied.
- Subjects will be given a 12 week supply of the study pills and reminded to take the pills as instructed.
- Subjects will be given a Study Diary and will be instructed to record any missed dose of their study pills, record how much standard of care naproxen taken, and to bring the Study Diary to next visit.

Visit 2/Week 4:

- Record: Weight (in pounds), blood pressure, history of lower back surgeries, medical history, and concomitant medications.
- Subjects will be asked to complete the following questionnaires:
 - RMDQ
 - PIQ-6
- Subjects will be asked “On a scale of 0-10, with 10 being the worst pain, what is your current level of pain”.
- Research staff will record whether subject had any side effects to report.
- Subjects will have their study medications refilled.
- Research staff will collect the subject’s Study Diary, issue them a new one, and remind them to bring it with them to the next study visit.
- Research staff will remind subjects to take the pills as instructed.
- Subjects will have the following research-driven blood test drawn via 1 venipuncture (5-10 mls, approximately 1-2 teaspoons of blood drawn for each test) which include:
 - Comprehensive metabolic panel (liver function, renal function, plasma glucose tests).
**Subjects who have had a comprehensive metabolic panel test within the one week prior to this visit will not need to have this test repeated unless they are abnormal.*
 - Complete Blood Count.
**Subjects who have had a complete blood count test within the one week prior to this visit will not need to have this test repeated unless they are abnormal.*

Visit 3/Week 8:

- Record: Weight (in pounds), blood pressure, history of lower back surgeries, medical history, and concomitant medications.
- Subjects will be asked to complete the following questionnaires:
 - RMDQ
 - PIQ-6
- Subjects will be asked “On a scale of 0-10, with 10 being the worst pain, what is your current level of pain”.
- Research staff will record whether subject had any side effects to report.
- Subjects will have their study medications refilled.
- Research staff will collect the subject’s Study Diary, issue them a new one, and remind them to bring it with them to the next study visit.
- Research staff will remind subjects to take the pills as instructed and to return the bottle to the research staff at the next visit.
- Subjects will have the following research-driven blood test drawn via 1 venipuncture (5-10 mls, approximately 1-2 teaspoons of blood drawn for each test) which include:
 - Comprehensive metabolic panel (liver function, renal function, plasma glucose tests).
**Subjects who have had a comprehensive metabolic panel test within the one week prior to this visit will not need to have this test repeated unless they are abnormal.*
 - Complete Blood Count.
**Subjects who have had a complete blood count test within the one week prior to this visit will not need to have this test repeated unless they are abnormal.*

Visit 4/Week 12 *SUBJECTS STOP TAKING STUDY PILLS AT THIS VISIT:

- Record: Weight (in pounds), blood pressure, history of lower back surgeries, medical history, and concomitant medications.
- Subjects will be asked to complete the following questionnaires:
 - RMDQ
 - PIQ-6
- Subjects will be asked “On a scale of 0-10, with 10 being the worst pain, what is your current level of pain”.
- Research staff will record whether subject had any side effects to report.
- Research staff will collect the subject’s Study Diary.
- Research staff will collect the study pills.
- Subjects will have the following research-driven blood test drawn via 1 venipuncture (5-10 mls, approximately 1-2 teaspoons of blood drawn for each test) which include:
 - Comprehensive metabolic panel (liver function, renal function, plasma glucose tests).
**Subjects who have had a comprehensive metabolic panel test within the one week prior to this visit will not need to have this test repeated unless they are abnormal.*
 - Complete Blood Count.
**Subjects who have had a complete blood count test within the one week prior to this visit will not need to have this test repeated unless they are abnormal.*

Final Visit 5/Week 16:

- Record: Weight (in pounds), blood pressure, history of lower back surgeries, medical history, and concomitant medications.
- Subjects will be asked to complete the following questionnaires:
 - RMDQ
 - PIQ-6
- Subjects will be asked “On a scale of 0-10, with 10 being the worst pain, what is your current level of pain”.
- Subjects will be asked if they are undergoing any other treatment for back pain, when the last treatment was, and whether or not they were satisfied.
- Subject will be asked if they have taken any medications for pain since their last visit.
- Research staff will record whether subject had any side effects to report.
- Subjects will have the following research-driven blood test drawn via 1 venipuncture (5-10 mls, approximately 1-2 teaspoons of blood drawn for each test) which include:
 - Comprehensive metabolic panel (liver function, renal function, plasma glucose tests).
**Subjects who have had a comprehensive metabolic panel test within the one week prior to this visit will not need to have this test repeated unless they are abnormal.*
 - Complete Blood Count.
**Subjects who have had a complete blood count test within the one week prior to this visit will not need to have this test repeated unless they are abnormal.*

DIRECTIONS FOR TAKING MEASUREMENTS:

Directions for weighing subjects: Have subject remove his/her shoes and empty pockets of any items prior to stepping on the scale. Weight should be recorded to the nearest ½ pound (for example 150.5#).

Directions for taking height: Have subjects remove their shoes before taking their height. Height should be recorded to the nearest 1/2 inch (for example 60.5”).

Directions for taking blood pressure: Have subjects sit for 5 minutes before taking blood pressure.

VISIT WINDOWS: Visits will have a 1 week visit window. If a subject fails to come in within this visit window, they will be instructed to bring in any unused study pills and removed from the study.

ADHERENCE TO STUDY ASSIGNMENTS: Adherence to study medication will be assessed via review of the “Study Medication Diary”. Compliance will be recorded both in paper format and in the electronic data collection tool. If a subject misplaces their Study Medication Diary, they will be asked to reproduce it from memory to the best of their ability. Subjects will be instructed to bring back all of the bottles regardless of whether there are empty or contain missed doses.

If a subject misses a dose, regardless of the amount, they will be encouraged to document this in their study diary and resume taking their pills. All subjects will remain in the study and continue with all the study related visits.

If a subject misplaces or loses their study medication, they will be instructed to return to the research department and will be given a new bottle of their assigned study medication. Since the research coordinator is not blinded, they will be able to give the medication that the subject was assigned.

If a subject forgets to bring their study medication in for their visit, they will be instructed to bring it in at their earliest convenience.

WITHDRAWAL PROCEDURES: If at any time during the study, the subject decides to withdraw consent or if the subject is withdrawn from the study by the investigator, they will be referred to their Primary Care Manager (PCM) to continue with standard of care treatment.

PREGNANCY: Subjects must agree to take precautions to prevent pregnancy during the course of this study due to the possible effect MSM may cause an unborn child. The only completely reliable methods of birth control are total abstinence or surgical removal of the uterus. Other methods, such as the use of condoms, a diaphragm or cervical cap, birth control pills, IUD, or sperm killing products are not totally effective in preventing pregnancy. In addition, women who are breastfeeding may not participate in this study.

If a subject unintentionally becomes pregnant, they will be instructed to cease taking their study pills, return their pill bottle and will be removed from the study.

DISPOSAL OF STUDY RELATED PILLS: Subjects will return any remaining study-related pills directly to the Research Coordinator or Principal Investigator. The Research Coordinator or Principal Investigator will be responsible for disposing of the study-related pills. The preferred method of disposal is to have the Pharmacy dispose of them. If the Pharmacy is unable to dispose of them, they will provide directions on safe disposal for the Research Coordinator or Principal Investigator to follow.

OTHER: Subjects will take their study pills daily and will be permitted to have the usual medical care for other co-morbid and acute conditions if applicable. Analysis described above using intention-to-treat principles for any missing data will be used (we will use the carry-forward method to impute missing data).

The placebo will be a capsule filled with rice flour, which does not increase the risks to subjects.

This study involves the use of an investigational product (IP) called Methylsulfonylmethane (MSM). This means that the product has not been approved by the Food & Drug Administration (FDA) for treating lower back pain. It is being given in a dose that does not increase the risk to the research subjects. There are no known risks associated with MSM as it is a compound granted GRAS (Generally Recognized As Safe) status by the United States Food and Drug Administration (more information can be found at <http://www.accessdata.fda.gov/scripts/cdrh/cfdocs/cfcfr/CFRSearch.cfm?fr=582.20>). The Sponsor-Investigator will report unexpected SAEs associated with the use of the drug to the FDA as specified at 21 CFR 312.32(c).

3.6.1. Interventions, Observations, or Data Sought:

We will assess the effect of 6000 mgs of MSM plus standard of care naproxen taken for 12 weeks plus one follow up visit on RMDQ, PIQ-6, pain level, comprehensive metabolic panel (CMP) and complete blood count (CBC) will be assessed at 4 week intervals.

3.6.2. Data Collection and Processing:

Data will be collected and recorded in a spreadsheet. At the conclusion of the study, all personally identifying information will be removed prior to analysis based on AFI 33-332, "The Air Force Privacy and Civil Liberties Program" and the "National Institute of Standards and Technology Special Publication (NIST SP 800-88) for the approved methods to destroy PII".

3.6.3. Setting: Mike O'Callaghan Military Medical Center at Nellis Air Force Base.

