2.1. Associate Investigators (AI): See form A-2 Study Personnel

2.2. Research Assistants (RA) & Coordinators (RC): See form A-2 Study Personnel

2.3. The research relevance of this protocol focuses on:

Diagnosis Treatment Medical Utilization/Managed Care Prevention Medical Readiness Other

2.4. Location(s):

- Collaborating Facilities: None.
- Air Force Sites seeking Regional IRB: Mike O'Callaghan Military Medical Center/Nellis Air Force Base, [name]
- List study sponsors: This study will be sponsored by Bergstrom Nutrition. The collaborative research will be executed in accordance with 15 USC 3710a through a Cooperative Research and Development Agreement, between the 99th MDG and Bergstrom Nutrition. The estimated fair market value of the support is \$17,570.00.

3. Research Plan:

3.1. Purpose:

The purpose of this study is to assess whether Methylsulfonylmethane (MSM) plus standard of care naproxen improves symptoms of lower back pain versus standard of care naproxen plus placebo.

3.2. Hypotheses, Research Questions or Objectives:

Does the addition of MSM to standard of care treatment improve symptoms of lower back pain assessed by Roland-Morris Disability Questionnaire (RMDQ), pain level, and Pain Impact Questionnaire (PIQ-6)?

3.3. Significance:

A lack of true clinical assessment of the usefulness of MSM in low back pain suggests that patients will continue to consume a product with a potential but unknown benefit. As a multidimensional approach to the treatment of low back pain is endorsed, the assessment of MSM on low back pain as an alternative or adjunctive therapy would be prudent. For this reason, we propose that a clinical trial be carried out to assess the impact of MSM on low back pain.

3.4. Military Relevance⁸¹:

Low back pain is a common complaint of Tricare beneficiaries. In 2012, chronic pain treatment accounted for an approximate annual cost of \$560-635 billion in direct medical treatment costs and lost productivity in the United States. Despite these costs, the response of each individual to standard treatments varies greatly, often being under treated. Within the military, responses to traditional treatments and lost productivity are no different than the civilian communities but may have a far more reaching consequence as service men and women are often unable to perform their duties fully or deploy due to pain.

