looked at its use during pregnancy). Prior to the recommendation to limiting the daily dose to 6 grams/day in humans, some physicians recommended up to 20 g/day, which approximates to 300 mg per kg/day⁷⁰.

Adverse Reactions^{13,24}: When dosed orally, nausea, diarrhea, bloating, headache, fatigue, insomnia, and difficulty concentrating have been reported. These adverse reactions however, do not appear to occur any more frequently in groups exposed to MSM than placebo in clinical trials¹³. There is no known drug-food, drug-drug, or drug-lab test interactions known²⁴.

Proposed use of MSM in Low Back Pain: As noted previously, MSM accounts for 4.1% of all nonvitamin, nonmineral CAM therapies used and is often cited as a remedy for back pain. Tant et al note that in a trial of glucosamine containing MSM, both yield symptomatic relief in patients with low back pain, individually and when taken together²⁵. Interestingly, trials such as that performed by Usha et al included MSM in the formulation of Glucosamine when assessing its impact on osteoarthritis¹⁴. However, additional information on the impact MSM may have on low back pain is lacking. Furthermore, of the 462 trials for low back pain registered with clinicaltrials.gov, none is designed to assess the impact of MSM on low back pain²⁶.

Patients continue to access information on CAM through a variety of sources. A lack of true clinical assessment of the usefulness of MSM in low back pain suggests that patients will continue to consume a product with a potential but unknown benefit. As a multidimensional approach to the treatment of low back pain is endorsed, the assessment of MSM on low back pain as an alternative or adjunctive therapy would be prudent. For this reason, we propose that a clinical trial be carried out to assess the impact of MSM on low back pain.

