3.6.8. Instrumentation: N/A

4.0. Human Subject Protection:

4.1. Recruitment:

All potentially eligible patients will be offered an opportunity to participate. Primary Care Managers (PCMs) who are not part of the research team will be informed about the study and provided information on the inclusion/exclusion criteria. PCM referrals and posted advertisements will be utilized for recruiting subjects to the study. Some patients may be patients of the PI or AI, however, they will have the study staff recruit their patients to prevent any misconception of coercion or undue influence. If a potential subject is identified by the treating PCM and is interested in obtaining more information about the study, the patient will either be provided a contact number to the Research Staff, the Research Staff will be given the potential subject's contact information by the PCM with the patient's oral or written authorization, or the PCM will come and get the Research Staff to speak with the patient directly.

4.2. Consent Processes:

The PI, AI, or Research Coordinators will obtain Informed Consent on this study. Informed consent and HIPAA Authorization will be sought in advance from each prospective subject. Informed consent will be appropriately documented. [32 CFR 219.117] After discussion with one of the investigators, the subject will be given the opportunity to consent. The investigator will provide a written copy of the consent form and allow the subject to read it, review it with the subject, and answer questions. The subject may decline to consent, and no pressure will be applied. If the subject consents to be enrolled in the study, the proper signatures will be obtained, and a copy given to the subject.

4.3 Participation Compensation: Subjects will not be paid for participation in this study.

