4.9.4. Injury Compensation: N/A

4.9.5. Data Safety Monitoring:

The trial will be conducted in compliance with this protocol, International Conference on Harmonization (ICH) Guidelines for Good Clinical Practice (GCP), and any applicable national and international regulatory requirements. The principal and associate investigators will be monitoring all aspects of the study in accordance with the appropriate regulations and will have regular meetings with periodic quality control of data documentation and collection. The objectives of the monitoring meetings will be:

- 1) To verify the prompt reporting of all data points, including reporting Serious Adverse Events (SAEs) and checking availability of signed informed consent,
- 2) To compare individual subject records, data pulls and/or the study source documents/case report forms (supporting data, laboratory specimen records and medical records to include physician progress notes, nurses' notes, subjects' hospital charts),
- 3) To ensure protection of study subjects, compliance with the protocol, and accuracy and completeness of records.

The principal investigator will be responsible for the protocol safety monitoring. The PI will make study documents (e.g., consent forms, data pulls) and pertinent hospital or clinical records readily available for inspection by the local IRB and oversight staff for confirmation of the study data.

[name], DO, Maj (Primary) and [name], Capt (Alternate) will be the research monitors assigned to this study.

5.0. Alternatives: The alternative is not to participate in this study.

6.0. Data Analysis:

6.1. Outcome Measures:

We will be utilizing stratified random sampling with proportionate allocation which will ensure that all parts of the population are represented in the sample.

Factors:

1. Subject Characteristics
 - a. Subject identification: nominal variable (1 ... n)
 - b. Gender: binomial variable (male, female)
 - c. Age: interval variable (years)
 - d. Height: interval variable (inches)
 - e. Weight: interval variable (pounds)
2. Treatment: nominal variable (Naproxen + MSM, Naproxen + placebo)
3. Time (5 repeated measures for each subject): nominal variable (0wk, 4wk, 8wk, 12wk, 16wk)
4. Outcomes
 - a. VAS: interval variable ^{72,73} (1-10 cm)
 - b. RMDQ: interval variable (0-11,18, or 24 depending on instrument used)
 - c. PIQ-6: interval variable (20-80)

6.2. Sample size estimation/power analysis:

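### The visit question on pain intensity does not name the low back, so the item can record other pain and dilute a low back effect by an unknown amount

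*Combined protocol and SAP*

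**What the plan says.** The body of the protocol (section 3.2) asks whether adding MSM will "improve symptoms of lower back pain assessed by Roland-Morris Disability Questionnaire (RMDQ), pain level, and Pain Impact Questionnaire (PIQ-6"). Pain level is thus one of three measures of low back pain symptoms.

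Section 3.6 scripts the pain item in the same words at Visits 1, 2, 3, 4 and 5: a 0-10 scale with 10 as the worst, and the question "what is your current level of pain". At Visits 1 and 5 the next item does name a site: "Subjects will be asked if they are undergoing any other treatment for back pain".

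Nothing else in the document limits the pain rating to the back. The directions for taking measurements cover weight, height and blood pressure. Section 3.6.8 reads "Instrumentation: N/A".

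The outcome list in section 6.1 does not contain this item. It has "VAS: interval variable" with a range of 1-10 cm, and no visit schedules a visual analogue scale.

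**The concern.** The trial's question concerns one site, and the scripted item concerns any site. A subject whose back has improved but who has a sore knee or a headache on the visit day can give the other pain as a truthful answer.

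Such subjects can be in the trial. Section 3.6.7 excludes comorbidity only when it is severe, and section 3.6 says subjects are "permitted to have the usual medical care for other co-morbid and acute conditions if applicable".

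At stake is how this one outcome can be read. Pain from elsewhere that MSM does not change adds variance and pulls the observed difference between arms towards zero. A weak result on the item could then reflect the wording as much as the treatment.

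**Working it through.** **Wording, set side by side**

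| Place | What is asked or named | Site named? |
|---|---|---|
| 3.2 objective | Pain level as a measure of low back pain symptoms | Yes, through the objective |
| 3.6, Visits 1-5 | Current pain, 0-10 | No |
| 3.6, Visits 1 and 5, next item | Other treatment for back pain | Yes |
| 3.6, measurement directions | Weight, height, blood pressure | Pain not covered |
| 6.1 outcomes | VAS, 1-10 cm | No, and not scheduled |

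The 0-10 question is therefore the only separately scheduled pain-intensity item. The RMDQ and PIQ-6 forms are attachments that are not shown, so 'only' does not extend to items inside them. The VAS in 6.1 also starts at 1, whereas the question allows 0.

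**The plan's own power figure**

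Inputs from section 6.2: f = 0.4, N = 68, m = 5 measures, correlation ρ = 0.8, critical F = 2.524097 on 4 and 63 df.

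- λ = f²·N·m / (1 + (m − 1)ρ) = 0.16 × 68 × 5 / 4.2 = 12.952.
- Power from the noncentral F(4, 63) = 0.80185, against 0.801850 printed.
- Upper tail of the central F at 2.524097 = 0.0495, against 0.049538 printed.

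Both reproduce. The point challenges neither figure, and whether this formula suits the planned test is a separate matter. It serves here only as a baseline.

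**Illustration 1: share of variance (assumed)**

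Suppose a share s of the score variance comes from other pain on which MSM has no effect, with the correlation unchanged. Then effective f = 0.4·√(1 − s) and λ = 12.952·(1 − s).

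| s | Effective f | λ | Power on this item |
|---|---|---|---|
| 0 | 0.400 | 12.952 | 0.80 |
| 0.10 | 0.379 | 11.657 | 0.75 |
| 0.20 | 0.358 | 10.362 | 0.70 |
| 0.30 | 0.335 | 9.067 | 0.63 |

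**Illustration 2: share of subjects (assumed)**

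Section 3.5 gives 2 points as the minimal clinically important difference on a numerical rating scale. If a share s of subjects rate another pain that MSM does not change, a true 2-point effect appears as 2(1 − s): 1.8 at s = 0.10 and 1.6 at s = 0.20.

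The two shares are different quantities, and the documents give a value for neither.

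**The case against.** **Context may supply the site.** Subjects are recruited for low back pain. The question follows two questionnaires, one of which (RMDQ) section 3.5 lists among low back pain function measures, and at Visits 1 and 5 it precedes a question about back pain. Sciatica and severe comorbidity are excluded. Many subjects will answer for their back. This stands, and it is why the size is unknown: the wording permits another pain to be rated but does not show that it will be. It does not remove the gap, because the script is meant to be read as written and Visits 2 to 4 lack even the neighbouring back-pain question.

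**A reader might infer bias against MSM.** Headache is listed among the MSM risks in section 4.6, and section 3.5 says "nausea, diarrhea, bloating, headache, fatigue, insomnia, and difficulty concentrating have been reported" with oral dosing. But 3.5 goes on to say that these reactions appear no more often with MSM than with placebo, and its paragraph on adverse side effects repeats this for a list that includes headache and indigestion. The documents support added noise in both arms, not a tilt against one.

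**A reader might infer that a null trial could not be interpreted.** Pain level is one of three outcomes, none is named primary, and the objective in the protocol summary lists only the RMDQ and PIQ-6. The limit applies to this item.

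**A reader might infer that a momentary rating is itself a defect and that a 7-day recall is required.** Current pain is a legitimate construct, and recall brings its own error. The gain is also easy to overstate. With an assumed between-subject SD of 2 and day-to-day SD w, one rating has (4 + w²)/(4 + w²/7) times the variance of an ideal seven-day average: 1.21 at w = 1 and 1.75 at w = 2. The implied between-visit correlation, 4/(4 + w²), is 0.80 and 0.50 respectively. Only w = 1 agrees with the 0.8 in section 6.2, and a recalled average is not an ideal one. Recall period is a choice between reasonable options and forms no part of this point.

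**Conclusion.** The point holds as a gap in construct validity on one of three outcomes. The scripted item does not name the site that objective 3.2 concerns, and no other text supplies it. The consequence the documents support is extra noise and possible dilution of a true low back effect on this item.

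The amount cannot be estimated from the documents. The ranges shown (power of about 0.75 to 0.63, or an apparent effect of 1.8 to 1.6 points in place of 2) depend on assumed shares and on MSM leaving the other pain unchanged. If MSM also eased that pain, as section 3.5 reports for osteoarthritis, the item would not be diluted in this way, and the improvement would be credited to the back. Both cases call for the same correction. The mismatch with the VAS in 6.1 should be settled at the same time, since the analysis section names a pain outcome that no visit collects.

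**What to change.** - In section 3.6, insert 'low back' before 'pain' in the 0-10 question at all five visits.
- In section 3.2, change 'pain level' to 'low back pain level'. For consistency, do the same where the term recurs in section 4 of the protocol summary and in section 3.6.1.
- In section 6.1, replace the VAS (1-10 cm) with the 0-10 low back pain rating actually collected.

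The cost is a short change to the visit form, with notice to the IRB. The drawback is that subjects already enrolled have a baseline only on the present wording. For them, keep the present item alongside the new one so that change from baseline remains available on a single wording.

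Section 3.6.4 gives study dates of June 2014 to June 2016 and the document is dated 4/5/2018, so collection may be finished. In that case the question should not be relabelled after the fact. Report the outcome as current pain, site unspecified, and state that limit beside the result.
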